#### 13.5 Subgroup Analyses

No examination of subgroups is planned.

#### 14 SAFETY ANALYSES

One of the study objectives is to assess the safety of tarloxotinib. Safety will be assessed by repeated clinical evaluations including adverse events (AEs), serious AEs (SAEs), suspected serious unexpected suspected adverse reactions, vital signs, physical examination, electrocardiograms (ECGs), clinical laboratory tests (serum chemistry, hematology, and urinalysis). All analyses of the safety data will be performed using the primary analysis set. All descriptive statistics (described in Section 9.1) will be presented by cohort and overall.

#### 14.1 Adverse Events

Safety will be assessed by repeated clinical evaluations including adverse events (AEs), serious AEs (SAEs), serious unexpected suspected adverse reactions (SUSARs), and deaths.

Safety data will be summarized descriptively. AEs will be summarized by severity, seriousness, and relationship to study drug. All AEs including the AE verbatim term and the associated AE MedDRA preferred term will be provided in the subject data listings. Incidence of treatment-emergent AEs will be summarized descriptively by cohort and total.

TEAEs are defined in Section 9.2.18.1. All reported AEs (including non-TEAEs) will be listed. Separate listings will be provided for suspected adverse reactions, unexpected events, SAEs, and serious unexpected suspected adverse reactions. All TEAE summary tables will present the number and percentages of subjects reporting TEAEs, unless otherwise specified. A summaries of TEAEs by severity, seriousness, and relation to study drug will be tabulated.

## 14.1.1 Overall Summary of TEAEs

Overall summary of TEAEs will be presented by cohort and overall. Subjects will be counted only once at the highest severity when summarizing TEAE by severity. The overall summary will include the following:

- Number (%) of subjects with any TEAEs
- Number (%) of subjects with any TEAEs by severity
- Number (%) of subjects with any serious TEAEs
- Number (%) of subjects with any related TEAEs
- Number (%) of subjects with any serious unexpected suspected adverse reactions

- Number (%) of subjects with any TEAEs leading to study drug discontinuation
- Number (%) of subjects with any AEs leading to death

#### 14.1.2 Summary of TEAEs by System Organ Class and Preferred Term

AEs will be summarized by MedDRA SOC and PT. Subjects can experience more than one AE per SOC and PT. At each level of subject summarization (SOC or PT or severity), subjects will be counted once if they reported at least one AE at that level (SOC or PT or severity). Each summary will be ordered by SOC alphabetically and by PT in descending order of the total incidence within each SOC. Summary tables will be created for each of the following types of AEs:

- TEAEs
- Severe (≥ Grade 3) TEAEs
- Related TEAEs
- TEAEs leading to study drug discontinuation
- Serious TEAEs
- Serious unexpected suspected adverse reactions
- TEAEs leading to death

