2.3.2 Clinical Trials

Study PR610-1001

A first-in-human Phase 1 clinical trial (Study PR610-1001) evaluated tarloxotinib administered as either a 1-hour or a 24-hour weekly intravenous (IV) infusion. The study was designed to determine the MTD and dose-limiting toxicities (DLTs) of tarloxotinib in patients with locally advanced or metastatic solid tumors. Twenty-seven patients received tarloxotinib administered weekly as a 1-hour infusion at doses ranging from 10 mg/m² to 200 mg/m² and 6 patients received tarloxotinib administered weekly as a 24-hour infusion at doses of 200 mg/m² or 335 mg/m². Of the patients who received tarloxotinib administered as a weekly 1-hour infusion, 6 patients received tarloxotinib at the recommended Phase 2 dose of 150 mg/m² tarloxotinib.

Confidential and Proprietary

DLTs with the 1-hour infusion included Grade 3 infusion-related reaction (150 mg/m²), Grade 3 facial pain (200 mg/m²), and Grade 4 QTc prolongation (200 mg/m²). An MTD of 150 mg/m² was declared for the 1-hour infusion duration. Other treatment-related AEs observed in the Phase 1 study included perioral paresthesia, musculoskeletal pain, nausea and vomiting, and dose dependent signs and symptoms of EGFR inhibition, notably skin rash, and diarrhea.

After the DLTs of Grade 3 facial pain (1) and Grade 4 QTc prolongation (1) were observed at 200 mg/m² administered as a 1-hour infusion, a 24-hour infusion duration was evaluated to determine if a reduced maximum peak plasma concentration (C_{max}) would reduce toxicities and allow higher weekly dosing. Three patients each were treated with a 24-hour infusion of tarloxotinib at 200 mg/m² or 335 mg/m². Treatment-related AEs were similar to those observed with the 1-hour infusion including nausea and diarrhea, skin rash and QT prolongation. A DLT of Grade 3 QTc prolongation was reported in 1 patient at 335 mg/m² at the 24-hour infusion duration.

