2.6 Potential Risks

Cancers harboring the mutations and fusions under evaluation in study RAIN-701 have been generally refractory to currently available therapies. Tarloxotinib is an investigational agent with no proven clinical benefits. As of the start of this clinical trial, tarloxotinib had been administered to 84 adults with a variety of cancer types. In the combined dataset of Studies TH-CR-601 and TH-CR-602 (n = 51), where tarloxotinib was administered as a 1-hour weekly IV infusion at a dose level of 150 mg/m², the most commonly reported AEs included ECG QT prolongation, diarrhea, fatigue, dermatitis, rash, pruritus, nausea, and cough. Infusion-related reactions characterized by flushing, urticarial skin rash, pruritus, and hypotension have been observed during and immediately following infusion of tarloxotinib. All patients receiving tarloxotinib should be instructed to seek immediate medical care in the event allergic symptoms develop.

Prolongation of the QT interval have been observed up to 4 hours following completion of tarloxotinib infusion. At the recommended dose of 150 mg/m², AEs of QT prolongation were reported by 35/51, 68.6% (19 of these patients experienced Grade 3 QTc prolongation). There was 1 patient who experienced a Grade 3/Grade 4 event at the 335 mg/m² dose level in the Phase 1 study). QT prolongation can infrequently lead to serious (rarely fatal) fast and irregular heart rhythms and other symptoms, such as severe dizziness and/or fainting, seizure, and palpitations. Patient eligibility criteria and monitoring have been implemented based on these past findings.

Due to the possibility of phototoxicity, patients should be instructed to avoid prolonged exposure to sunlight while on study treatment and when exposure cannot be avoided to use a broad-spectrum sunscreen.

Please refer to the most recent version of the Tarloxotinib Investigator's Brochure for the most current understanding and management of the potential risks associated with the use of tarloxotinib.

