AEs must be reported using standard medical terminology. The use of abbreviations (standard and nonstandard) should be avoided to help ensure a clear understanding of the event. An example of a standard abbreviation that may have several meanings is "MI" which could mean "myocardial infarction" or "mitral insufficiency." All AE terms will be coded using a standardized dictionary (i.e., Medical Dictionary for Regulatory Activities [MedDRA®]). Generally, when reporting a well-known and understood condition, it is preferable to report the overall diagnosis rather that the individual signs and symptoms; the exception to this rule in this study is when the patient experiences an infusion reaction (i.e., infusion-related reaction). The term "intermittent" should be avoided as the duration and incidence of events helps in understanding the safety profile of the study drug.

8.2.2 **Adverse Event Severity**

AEs will be reported at the highest experienced. AE severity will be graded according to NCI CTCAE v5.0. A copy of the document will be provided to investigational sites and an electronic version is available at:

https://ctep.cancer.gov/protocolDevelopment/electronic applications/docs/CTCAE v5 Quick R eference 8.5x11.pdf

Events not listed in NCI CTCAE will be graded according to the criteria described in Table 10.

Confidential and Proprietary

Table 10: Severity Grading Guideline for Adverse Events Not Listed in NCI CTCAE

Adverse Events Not Listed in NCI CTCAE v5.0			
Grade	Description		
1	Mild; Asymptomatic or mild symptoms; Clinical or diagnostic observations only; Intervention not indicated		
2	Moderate; Minimal, local or noninvasive intervention indicated; Limiting age-appropriate instrumental activities of daily living*		
3	Severe or medically significant but not immediately life-threatening; Hospitalization or prolongation of hospitalization indicated; Disabling; Limiting self-care activities of daily living**		
4	Life-threatening consequences; Urgent intervention indicated		
5	Death related to adverse event		

Adapted from NCI CTCAE v5.0

NCI CTCAE = National Cancer Institute Common Terminology Criteria for Adverse Events

Note: A semicolon indicates "or" within the description of the grade.

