8.4 Reporting Infusion-related Reactions

Infusion-related reactions (IRRs) are defined as "a disorder characterized by adverse reaction to the infusion of pharmacological or biological substances." The incidence and severity or IRRs will be collected in the eCRF designed to collected tarloxotinib infusion details; individual signs and symptoms of IRRs will be reported as AEs. Investigators will indicate which reported AEs were part of an IRR.

Confidential and Proprietary

Table 11: Severity Grading Guideline for Infusion-Related Reactions

Infusion-Related Reactions		
Grade	Description	
1	Mild transient reaction; infusion interruption not indicated; intervention not indicated	
2	Therapy or infusion interruption indicated but responds promptly to symptomatic treatment (e.g., antihistamines, nonsteroidal anti-inflammatory drugs, narcotics, intravenous fluids); prophylactic medications indicated for ≤ 24 hours	
3	Prolonged (e.g., not rapidly responsive to symptomatic medication and/or brief interruption of infusion); recurrence of symptoms following initial improvement; hospitalization indicated for clinical sequelae	
4	Life-threatening consequences; Urgent intervention indicated	
5	Death	

Adapted from National Cancer Institute Common Terminology Criteria for Adverse Events v5.0

Note: A semicolon indicates "or" within the description of the grade.

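### Infusion reactions reach the AE data as separate signs, and no planned SAP table puts them back together, so their incidence and grade would not be reliably shown

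*SAP*

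**What the plan says.** Protocol 8.2.1 prefers the overall diagnosis as the AE term for a well-understood condition, and then adds that "the exception to this rule in this study is when the patient experiences an infusion reaction". Protocol 8.4 sets out three steps for such a reaction:

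- The reaction itself: "The incidence and severity or IRRs will be collected in the eCRF designed to collected tarloxotinib infusion details".
- Its components: "individual signs and symptoms of IRRs will be reported as AEs".
- The link between the two: "Investigators will indicate which reported AEs were part of an IRR".

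Protocol Table 11 grades the reaction as a whole.

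The protocol describes IRR as a known risk. Section 2.3.2 reports that "DLTs with the 1-hour infusion included Grade 3 infusion-related reaction (150 mg/m²"), and Section 6.7 starts every patient at that dose. Section 2.6 states: "Infusion-related reactions characterized by flushing, urticarial skin rash, pruritus, and hypotension have been observed during and immediately following infusion of tarloxotinib". Table 8 is a treatment guideline for IRRs alone.

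On the analysis side, SAP 14.1.2 states "AEs will be summarized by MedDRA SOC and PT", and SAP 14.1.3 repeats the tables by preferred term alone. SAP 14.1 and 14.1.1 add overall counts by severity, seriousness and relationship, together with listings of all AEs by verbatim and preferred term.

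**The concern.** The protocol splits this one event into parts and also collects what is needed to reassemble it. The SAP plans output from the parts only. Two quantities that a safety reader would look for are then missing: the number of subjects with at least one IRR, and the highest grade of the reaction.

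This matters because IRR was dose-limiting at the dose used here, and because SAP Section 4 presents the safety analysis as a full one even though the report is abbreviated. QTc prolongation, the other toxicity with its own treatment-guideline table for a single named event, gets dedicated categorical summaries in SAP 14.4. IRR gets none.

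**Working it through.** The plan states no IRR figure to reproduce, so the check sets the two documents side by side and then illustrates the ambiguity on assumed counts.

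**1. Where each IRR item goes**

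| Collected under Protocol 8.4 | Planned SAP output that uses it |
|---|---|
| IRR incidence and severity, infusion eCRF | None. SAP 12.1 reports cycles and dose intensity. SAP 9.2.16.2 counts an interrupted infusion as one infusion, and no summary of interruptions is planned. |
| Component signs as AEs | SOC/PT and PT tables, overall TEAE summary, AE listings |
| Flag linking an AE to an IRR | None. The listings described in SAP 14.1 name verbatim and preferred terms, not the flag. |

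SAP 14.1.1 to 14.1.3 contain no grouped IRR term, IRR table or IRR listing.

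**2. Grade**

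The severe-TEAE tables in SAP 14.1.2 and 14.1.3 take AEs of Grade 3 or higher, and each component sign carries its own grade. Protocol Table 11 grades the whole reaction by features such as slow response to treatment, recurrence after improvement, or need for hospitalization. A reaction can meet Grade 3 on those features while each of its signs is graded lower. It would then be missing from the severe-TEAE tables.

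**3. Can the sign rows be decoded?**

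Not from the tables. Protocol 2.3.2 reports rash in 7/51 = 13.7% and pruritus in 5/51 = 9.8% of patients in the two earlier Phase 2 studies, listed there as skin disorders. A row for either sign may therefore mix IRR and non-IRR events.

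**4. Illustration on assumed counts (not trial data)**

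Inputs: 11 + 22 + 8 = 41 treated subjects (SAP Table 1) and the four signs named in Protocol 2.6. Assume that each sign's row shows 2 subjects (2/41 = 4.9%) and that every IRR shows at least one of these signs. Intervals are exact (Clopper-Pearson).

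- No sign was part of an IRR: 0/41 = 0% (95% CI 0 to 8.6).
- The same two subjects had all four signs in an IRR: 2/41 = 4.9% (95% CI 0.6 to 16.5).
- All signs were in different subjects and all were IRRs: 4 × 2 = 8, so 8/41 = 19.5% (95% CI 8.8 to 34.9).

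The same four PT rows fit all three cases.

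**The case against.** Much can fairly be said for the SAP:

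- **No protocol commitment is broken.** Protocol 9.7 asks for no IRR summary, and Protocol 8.5 gives special-interest status to QT prolongation, not to IRR. Section 15 therefore had no departure to record. This stands: the point concerns a gap in the output, not a breach.
- **The component events are not lost.** They are counted and listed, and SAP Section 4 allows unplanned analyses to be documented in the CSR. This also stands, but a listing of signs without the flag does not give an incidence.
- **The trial stopped early, for business reasons, and the report is abbreviated.** This lowers the stakes. The SAP, however, uses the abbreviation to drop efficacy testing and protocol deviations, not to narrow safety.

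A reader might also infer more than the documents support:

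- *That the SAP tabulates AEs only by preferred term.* It also tabulates by SOC and by overall severity, seriousness and relationship. None of these groups events by IRR.
- *That an IRR row must be empty.* Protocol 8.2.1 words the general rule as a preference, and 8.4 does not forbid also entering the diagnosis. Under strict adherence the row would be empty. If some sites entered the diagnosis it would be partial. Either way it is unreliable.
- *That one reaction is spread over a known number of organ classes.* The documents contain no MedDRA mapping. The argument needs only separate PT rows.
- *That the understatement can be sized at 1/41 = 2.4 percentage points.* That is the weight of any one subject for any event and says nothing about IRR in this trial.
- *That Table 8 is a dose-reduction table.* It is a treatment guideline. Dose levels are in Table 6, where IRR shares a column with other toxicities.
- *That the data are certainly in hand.* The CRF is not among the documents, and SAP Section 15 records that other protocol-specified items were not collected.

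**Conclusion.** The point holds as a gap in planned safety reporting. If Protocol 8.2.1 and 8.4 are followed, IRRs enter the AE data as component signs, and nothing in SAP 14.1 or 12.1 reassembles them. The planned tables would not reliably show IRR incidence or whole-reaction grade, and a Grade 3 reaction could be missing from the severe-TEAE tables.

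Its size in this trial is unknown, because the documents contain no IRR counts. The 0% to 19.5% range rests wholly on the assumed rows and shows only that the planned tables cannot separate very different incidences. The conclusion assumes that sites reported signs as instructed. Whether it can be repaired depends on the infusion eCRF fields and the flag having been captured.

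**What to change.** First, confirm that the infusion eCRF holds IRR incidence and severity and that the AE-to-IRR flag was recorded. The SAP (14 October 2022) postdates database lock (23 April 2021), so the table has to come from what was captured.

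If they were captured, add to SAP 14.1:

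- A table of the number (%) of subjects with at least one IRR, by highest Table 11 grade, by cohort and overall (N = 41), from the infusion eCRF.
- A listing of the component AEs flagged as part of an IRR.
- A footnote to the PT tables saying that the signs of an IRR are reported as separate terms, with a pointer to the new table.

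If they were not captured, say so in SAP Section 15, as is already done there for ALP.

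This is a cheap improvement. If the data exist, it costs a short SAP edit, one table and one listing, with no new data collection.

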#### 14.1.3 Summary of TEAEs by Preferred Term

AEs will be summarized by MedDRA preferred term (PT). Subjects can experience more than one AE per PT. At each preferred term, subjects will be counted once if they reported at least one AE at that level (PT). Each summary will be ordered by PT in descending order of the incidence. Summary tables will be created for each of the following types of AEs:

- TEAEs
- Severe (≥ Grade 3) TEAEs
- Related TEAEs
- TEAEs leading to study drug discontinuation
- Serious TEAEs
- Serious unexpected suspected adverse reactions
- TEAEs leading to death

#### 14.2 Clinical Laboratory Evaluation

Results for clinical laboratory parameters (serum chemistry and hematology), vital signs, ECGs, and physical examinations will be summarized by cohort and combined and by study visits.

Descriptive summary statistics in observed values as well as changes from baseline will be

presented. In addition, thresholds of marked laboratory abnormalities based on NCI CTCAE v5.0 will be summarized by worst grade shift from baseline (see Appendix B).

Table 7 shows clinical laboratory assessments (hematology, chemistry, and urinalysis) that were performed performed. Chemistry and hematology laboratory parameters will be summarized by cohort and scheduled visit. Urinalysis assessments will be listed but not summarized due to their qualitative nature.

**Table 7** Clinical Laboratory Parameters

Chem	istry	Hematology	Urinalysis
Sodium	Creatinine	Hematocrit	Specific gravity
Potassium	Total Bilirubin	Hemoglobin	Protein
Chloride	AST/SGOT	WBC count	Glucose
Bicarbonate	ALT/SGPT	Neutrophils	Ketones
Calcium	<del>ALP</del> ‡	Lymphocytes	Urobilinogen
Magnesium	Albumin	Monocytes	Occult blood
Phosphorous	Total protein	Eosinophils	Microscopic sediment
			evaluation ‡
Glucose		Basophils	
Blood urea nitrogen		Platelet count	WOCBP only:
			β-HCG§

ALT = alanine aminotransferase; ALP = alkaline phosphatase; AST = aspartate aminotransferase; HCG = β-human chorionic gonadotropin pregnancy; SGOT = serum glutamic-oxaloacetic transaminase; SGPT = serum glutamic pyruvic transaminase; WBC = white blood count; WOCBP = women of child-bearing potential

Numeric results will be summarized using (6-point) descriptive statistics at baseline and at each scheduled post-baseline time point, unless otherwise specified. Changes from baseline will also be summarized by scheduled time point, where available. Selected laboratory results will be listed with CTCAE reference ranges.

#### 14.3 Vital Signs

Descriptive statistics for pulse rate, respiratory rate, temperature, weight, and blood pressure (systolic and diastolic) including baseline values and change from baseline values, will be summarized by cohort and scheduled time point. All vital signs parameters will be listed.

‡ Alkaline phosphatase and microscopic sediment evaluation will neither be listed nor summarized due to lack of data § β-HCG pregnancy test may be collected as a serum, urine, or urine dipstick assessment

#### 14.4 12-Lead Electrocardiogram

Electrocardiogram (ECG) data, such as clinical interpretation of ECGs, heart rate (HR) values, and interval assessments of QRS duration, PR interval, QT interval, and the Fridericia's corrected value of the interval between the Q and T waves on the ECG tracing (QTcF) will be listed. Descriptive statistics for observed values and change from baseline at each scheduled time point will be presented for these 12-lead ECG interval and HR assessments will be presented as actual values and as changes from the baseline values by 6-point descriptive summary statistics (n, mean, SD, median, minimum, and maximum). The numbers and percentages of subjects who meet categorical analyses such as the following criteria at each scheduled ECG time point will be presented.

- Absolute QTcF interval:
  - o QTcF interval < 450
  - o QTcF interval 451 to 480 msec
  - o QTcF interval 481 to 500 msec
  - o QTcF interval  $\geq$  501 msec
- Change from predose baseline in QTcF interval:
  - $\circ \le 30 \text{ msec}$
  - o 31 to 60 msec
  - o 60 msec

The numbers and percentages of subjects meeting each criterion will be summarized for each ECG time point, as well as for each subject overall at any time.

Abnormal ECG findings not present at the pre-dose baseline will be summarized as the number of subjects with each finding at 1 or more ECG times. Descriptive waveform morphology changes will be provided.

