9.7.1 Cardiac Safety

Electrocardiogram parameters (PR interval, QRS interval, QT interval corrected for heart rate by Fridericia's formula [QTcF] and Bazett's formula [QTcB], and heart rate) will be presented as actual values and as changes from the baseline values by summary statistics (number, mean, standard deviation, median, minimum, and maximum). Each of these will be presented at each scheduled ECG time, along with their 2-sided upper 90% CI, using a mixed effects analysis of variance. The primary statistical model will include the effects of patient and ECG time. The numbers and percentages of patients who meet categorical analyses such as the following criteria at each scheduled ECG time point will be presented.

- Absolute QTc interval:
 - o OTc interval < 450
 - o OTc interval 451 to 480 msec
 - o QTc interval 481 to 500 msec
 - QTc interval \geq 501 msec
- Change from predose baseline in QTc interval:
 - o < 30 msec
 - o 31 to 60 msec
 - \circ > 60 msec

The numbers and percentages of patients meeting each criterion will be summarized for each ECG time point, as well as for each patient overall at any time. In addition, a central tendency analysis of the ECG parameters will be performed.

Abnormal ECG findings not present at the predose baseline will be summarized as the number of patients with each finding at 1 or more ECG times. Descriptive waveform morphology changes will be provided. Additional ECG analyses may be conducted and will be provided in a separate SAP.

Confidential and Proprietary

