#### 4 PURPOSE OF THE ANALYSIS PLAN

This statistical analysis plan (SAP) pre-specifies the statistical analysis methods for supporting the completion of the abbreviated clinical study report (CSR) of Study RAIN-701 for investigational product tarloxotinib, a novel drug candidate designed to treat subjects with advanced solid tumors with qualifying genetic mutations and/or fusions. The study intended to enroll up to 215 subjects across 5 cohorts but was discontinued early on the basis of a business decision made by the sponsor. At the time of the database lock for RAIN-701 (23 April 2021), 41 subjects were enrolled. This SAP will be used to conduct a comprehensive safety analysis and summarize the available efficacy data collected during the study. The primary, secondary, and efficacy analyses planned in the protocol may not be appropriate or possible based on the available data. The planned analyses identified in this SAP may be included in future manuscripts.

The analysis methods described in this plan are considered *a posterior*, in that they have been defined after the clinical database lock. Exploratory analyses that are not defined in this SAP may be performed to support the clinical development program. Any post-hoc or unplanned analyses that are performed for the CSR, but not defined in this SAP, will be documented in the CSR. Changes from the planned analyses stated in the study protocol are described in Section 15. Should the SAP and the protocol be inconsistent with respect to any further planned analyses, the language of the SAP is governing.

Version 1.0, 14 October 2022

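### SAP 14.4 drops the protocol's mixed model and 90% CI for QTcF, along with QTcB and the central tendency analysis, and Section 15 does not list or justify the change

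*SAP*

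**What the plan says.** Protocol 9.7.1 (Cardiac Safety) covers PR, QRS, QTcF, QTcB and heart rate, as values and as changes from baseline. Besides summary statistics, these are to be presented at each scheduled ECG time "along with their 2-sided upper 90% CI, using a mixed effects analysis of variance". The model is named: "The primary statistical model will include the effects of patient and ECG time". Threshold categories follow, and then a separate item: "In addition, a central tendency analysis of the ECG parameters will be performed".

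SAP 14.4 (12-Lead Electrocardiogram) says the ECG assessments "will be presented as actual values and as changes from the baseline values by 6-point descriptive summary statistics". It keeps the threshold categories for QTcF: "The numbers and percentages of subjects meeting each criterion will be summarized for each ECG time point", and also for each subject at any time. It keeps new abnormal findings, waveform morphology and listings. It has no model, no confidence interval, no QTcB and no central tendency analysis under that name.

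On departures from the protocol, SAP Section 4 states: "Changes from the planned analyses stated in the study protocol are described in Section 15". The same section says the SAP governs where the two documents disagree, and that it supports a comprehensive safety analysis.

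**The concern.** Protocol 2.5 calls QT prolongation the main identified risk of the drug. In the two earlier Phase 2 studies (Protocol 2.3.2) it was reported in 35 of 51 patients, 19 of them at Grade 3, with mean maximum QTcF changes of 51 and 55 msec. For this risk the protocol chose an interval estimate of the mean change at each ECG time. The SAP gives a point estimate without an interval. Because the SAP governs, the protocol's analysis will not be done unless the SAP is changed.

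Two things are at stake. The first is a stated precision for the mean QTcF change, which matters most in the small cohorts. The second is traceability: a reader of the abbreviated report who relies on Section 15 would not learn that a named primary ECG model had been planned and left out.

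**Working it through.** **1. Side by side.**

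| Element | Protocol 9.7.1 | SAP 14.4 | SAP Section 15 |
|---|---|---|---|
| Descriptive statistics, values and changes | yes | yes (six statistics) | n/a |
| QTc categories, abnormal findings, morphology | yes | yes (QTcF) | n/a |
| Mixed model with patient and ECG time | yes | no | not mentioned |
| 90% CI at each scheduled ECG time | yes | no | not mentioned |
| QTcB | yes | no | not mentioned |
| Central tendency analysis | yes | not named | not mentioned |

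Section 15 covers the Per Protocol set, the timing of response confirmation, laboratory tests not collected, laboratory units and ranges, and MedDRA versions. It goes down to small items and has no ECG entry.

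**2. Is the omission explained elsewhere?** SAP 5.1.2 and 13.3 drop the association between plasma exposure and cardiac repolarization. That is a different analysis. SAP 5.1, 9.1 and 13.1 replace formal analysis by description because the sample is small and tests would be underpowered, but all three speak of efficacy. Protocol 9.7.1 mentions a separate SAP, but only for additional ECG analyses, and SAP 14.4 cites no such document.

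**3. Are intervals dropped throughout?** No. SAP 13.2 gives an exact 95% CI for ORR by cohort, and 13.3.2 gives 95% CIs for median PFS and OS, although Section 15 calls efficacy not interpretable. An ORR interval is therefore planned for the 8 subjects of Cohort C, while no QTcF interval is planned even for all 41.

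**4. What precision would the interval have?** Neither document states a precision figure for QTcF, so there is none to reproduce.

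Inputs: SAP Table 1 gives Cohort A 11, Cohort B 22 and Cohort C 8, total 41. The SD of QTcF change is not given and is assumed to be 12 to 30 msec.

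Formula, for one time point with complete data: half-width = t(0.95, n−1) × SD / √n.

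| Group | n | t | SD 12 | SD 20 | SD 30 |
|---|---|---|---|---|---|
| All | 41 | 1.684 | 3.2 | 5.3 | 7.9 |
| Cohort B | 22 | 1.721 | 4.4 | 7.3 | 11.0 |
| Cohort A | 11 | 1.812 | 6.6 | 10.9 | 16.4 |
| Cohort C | 8 | 1.895 | 8.0 | 13.4 | 20.1 |

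Example: 1.684 × 30 / √41 = 50.52 / 6.403 = 7.9 msec. With a mean change of 55 msec and SD 20, the interval is 49.7 to 60.3 msec for 41 subjects and 41.6 to 68.4 msec for 8. These are simple t intervals; the mixed model could differ.

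**5. Why 12 to 30.** Under a normal distribution, SD = (60 − mean) / z, where z matches the share of patients with a change above 60 msec. The pooled 34% (z = 0.412) gives 5 / 0.412 = 12.1 with mean 55 and 9 / 0.412 = 21.8 with mean 51. Study TH-CR-601's own 38% (z = 0.305) with its mean of 51 gives 9 / 0.305 = 29.5. This only brackets the assumption. The first two figures mix a pooled share with single-study means, and none of the shares is tied to the time point of the mean.

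**The case against.** The strongest reply is that the trial stopped early, and the SAP was written after database lock to support an abbreviated report. Protocol Section 9, Section 9.7 and the synopsis all describe safety data as summarized descriptively, so a descriptive ECG section is defensible. SAP 14.4 is also fuller than means alone: it gives n, SD, median, minimum and maximum with category counts. From n and SD a reader can compute exactly the simple intervals shown above. The six statistics might also be said to cover central tendency.

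Much of this stands. A reader might infer that QT results will appear with no measure of spread; the SAP does not support that. What cannot be rebuilt from its tables is the model-based interval, which uses each patient's repeated measurements and allows for some patients missing at some times.

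The general descriptive statements do not displace 9.7.1. That is the specific cardiac section, it names a primary model, and it adds the central tendency analysis as a further item. Early termination could be a reason for dropping the model, but the SAP does not give it for ECG.

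A reader might also infer that the earlier studies fix the SD. They do not: the figures are incomplete and give roughly 12 to 30 msec depending on which are combined.

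Nor does the model cure every later-visit problem. Protocol Table 7 ties dose reduction and discontinuation to QTcF, so later time points mix doses and a selected group of patients. A model with patient and time does not by itself remove that.

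**Conclusion.** The concern holds in this form. SAP 14.4 departs from Protocol 9.7.1 by leaving out the mixed model, the 90% CI, QTcB and the central tendency analysis. Section 15 does not disclose the departure, and no stated reason covers it. SAP Section 4 does not say that Section 15 lists every change, but a named primary model for the main identified risk plainly belongs there.

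The loss is one of stated precision: about ±3 to ±8 msec overall and about ±8 to ±20 msec in Cohort C, for an assumed SD of 12 to 30 msec, complete data and one time point. Against earlier mean changes of 51 and 55 msec the overall estimate would be usefully precise, so small numbers are no reason to withhold the interval.

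A reader might go further and infer that the interval would change whether the drug is judged to prolong QT. The documents do not support that: the earlier effects are large compared with the overall half-width, and no decision rule depends on the bound. The change is worth making for completeness and for fidelity to the protocol.

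**What to change.** In SAP 14.4, restore the protocol's model, with patient and ECG time, for QTcF change from baseline. Report two-sided 90% CIs at the scheduled ECG times, overall and by cohort where numbers allow. Label it as the protocol-specified analysis, since the SAP postdates database lock.

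Clarify the protocol's phrase about a two-sided upper interval. If only the upper limit of a two-sided 90% interval is meant, it equals a one-sided 95% bound, and the table should say so.

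A baseline QTcF covariate would be an addition to 9.7.1 and should be labelled so. The same holds for a restriction to Cycle 1 and Cycle 2 Day 1, where the full ECG set is scheduled for everyone. There is a reason to consider the restriction: under Protocol 6.9.2 the later 4-hour ECG is only for patients with prolonged QTcF, so a later 4-hour mean may describe a selected group. SAP 6.3.2.4 describes that ECG as done at all treatment visits after Cycle 1, and the two passages must be reconciled before later 4-hour summaries are interpreted.

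List in Section 15, with reasons, any element still dropped, such as QTcB or the central tendency analysis. A Section 15 entry alone would repair the disclosure but leave the main risk without an interval.

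The cost is one model and one table on data already locked, plus a short entry in Section 15.
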